1304 for 4 or 2 weeks, respectively, all groups switch to use of the alternative technology (Figure 1).

The primary purpose of this pilot study is to evaluate the safety and efficacy of combining SGLT2 inhibitors with closed loop control, and to gauge the effect size of the outcomes listed below. Nevertheless, the projected sample size of N=40 (N= 60 recruited) participants is expected to

- 1308 results in statistically significant differences on some outcomes:
- 1309 Primary Outcome: CGM-measured time in the target range 70-180mg/dl (TIR) during the day;
- 1310 Hierarchical secondary outcomes: 24/7 CGM time in range <70mg/dl; 24/7 CGM-measured
- 1311 average glucose; CGM-measured glucose variability (coefficient of variation, CV) during the day;
- 1312 risks for hypo- and hyperglycemia.

1313 Analysis Overview: The overall analysis will follow Intention-to-treat (ITT) approach, with each 1314 participant analyzed according to the treatment assigned by initial randomization. The study 1315 design includes repeated measures on all outcomes; thus, we will use a linear mixed-effect model 1316 that corresponds well to this structure. The mixed model will use "Subject" as a random factor 1317 and "Group" as a fixed factor, e.g. using the Linear Mixed Models procedure in SPSS. We should 1318 note that similar results may be generated by repeated measures ANOVA, but mixed models 1319 handle missing data better (e.g. ANOVA only uses listwise deletion, which could reduce power 1320 and introduce bias towards study completers). A mixed model is also more flexible and will allow us to address additional questions, such as clustering of subjects or introducing time between 1321 1322 assessments as a continuous variable.

1323 Data Sources: Continuous glucose monitoring (CGM) data acquired every 5 minutes during the 1324 baseline and throughout the study. CGM data will be used to compute established metrics of 1325 glycemic control (e.g. time in ranges), risks for hypo- and hyperglycemia, e.g. the Low and High 1326 BG Indices (LBGI/HBGI), and CV, as recommended by the Consensus on Use of CGM, to which our 1327 team contributed substantially.

- Handling of Missing Data: All randomized participants who have at least 50% of their CGM readings during the study period will be included in the analysis. Occasional missing CGM data do occur during normal CGM use and these values will be ignored when summary CGM metrics (e.g. percent times in range, LBGI, HBGI) are computed. Typically, CGM data are voluminous and the percent of missing values is low; thus no imputation would be required. For example, in the recently completed multi-center Protocol 3 of the International Diabetes Closed Loop Trial, N=168 subjects (of N=168 recruited) completed the entire 6-month protocol, and CGM data were
- 1335 available 96% of the time [15] (Table 1).
- 1336 Safety outcomes will be reported for all enrolled participants, irrespective of whether the 1337 subjects were randomized or the study was completed.
- 1338 Data Analysis: The objectives of this study are addressed by different sub-analyses of our general
 1339 analytical scheme, as follows:
- 1340Objective 1: Effect of adding Empagliflozin to predictive low glucose suspend (Basal IQ 21341weeks) and closed-loop control (Control IQ 4 weeks) will be assessed by the study1342randomized design (Figure 1). In this design we will have N=20 participants on Empagliflozin1343and N=20 participants off Empagliflozin, beginning with Control IQ and then switching to1344Basal IQ, or beginning with Basal IQ and then switching to Control IQ. This analysis will be1345done using the baseline data as covariates in a general linear model.
- 1346Objective 2: CGM-measured effect of Empagliflozin will be assessed using the baseline CGM1347data, (between Visits 2 and 3) via direct contrast between the two Experimental and two1348Control groups (N=20 participants in Groups 1-2 vs 20 participants in Groups 3-4);
- 1349Objective 3: CGM-measured effects of Empagliflozin added to Basal IQ will be assessed by1350direct comparison of the Experimental vs Control groups during the Basal IQ sessions (N=201351participants per arm will be available to this analysis);
- 1352Objective 4: CGM-measured effects of Empagliflozin added to Control IQ will be assessed1353by direct comparison of the Experimental vs Control groups during the Control IQ sessions1354(N=20 participants per arm will be available to this analysis);
- 1355 To preserve the overall type 1 error, a hierarchical testing procedure will be used: if the primary 1356 analysis for CGM-measured TIR 70-180mg/dL during the day is statistically significant (p < 0.05), 1357 then testing will proceed to the next outcome metric in the following order: CGM-measured 24/7 1358 percent time <70mg/dL; CGM-measured average glucose; CGM-measured CV during the day; 1359 LBGI and HBGI. This process will continue iteratively moving to the next variable down on the list 1360 until a non-significant result ($p \ge 0.05$) is observed, or all variables have been tested. If a non-1361 significant result is encountered, then formal statistical hypothesis testing is terminated and any 1362 variables remaining on the list become exploratory.

1363 **15.2 Sample Size**

1364 Sample Size Determination is based on data from our Protocol 3 of the recently completed iDCL Trial (Table 1) conducted with the same algorithm in the same population. The Pre-Post changes 1365 in TIR in Table 1indicate effect size of >0.7 of Control IQ compared to SAP. Knowing the action of 1366 Basal IQ and Control IQ, and the action of Empagliflozin, we can assume that Empagliflozin will 1367 1368 double the effect of Basal IQ and Control IQ during the day and will preserve their benefits overnight. This, a 1:1 randomization into two Experimental vs. two Control groups and N=20 1369 participants per study arm, yields a sample size on N=40 subjects to complete the study. This 1370 1371 sample size was computed using the G*Power 3 software under the assumptions of power=90% 1372 and type 1 error α =0.01, further reinforcing the feasibility of the hierarchical analyses described above. In our experience with long-term AP studies, we observe attrition rate of 20%, with most 1373 dropouts occurring during the baseline prior to randomization. Thus, the recruitment sample size 1374 was increased to N=60 to accommodate up to 20% attrition rate without sacrificing statistical 1375 1376 power. We should also note that technology improvement appears to increase the retention rate 1377 in recent large-scale trials. For example, it the iDCL protocol 3, only 2 out of 170 recruited 1378 participants dropped out and all 168 randomized participants completed the 6-month study.

Table 1: Glycemic control	Baseline (2 weeks)		Post-Randomization (26 weeks)			
results from Protocol 3: N=168 patients who used Control IQ for 6 months	CLC	SAP	CLC	SAP	Differenc e	p value
CGM use during the study			97%	96%		
Percent below 70 mg/dL	3.59 ± 3.39%	2.82 ± 2.53%	1.59 ± 1.15%	2.25 ± 1.46%	-0.88%	<0.0001
Percent 70-180 mg/dL (study primary outcome)	60 ± 17%	59 ± 14%	71 ± 12%	59 ± 15%	+11%	<0.0001
Percent above 180 mg/dL	36 ± 19%	38 ± 15%	27 ± 12%	39 ± 15%	-10%	<0.0001

Percent above 250 mg/dL	12.4 ± 12.8%	11.9 ± 9.9%	7.0 ± 6.7%	12.4 ± 10.3%	-5.5%	<0.0001
HbA _{1c}	7.4%	7.4%	7.06%	7.4%	-0.33%	=0.0014
Mean glucose [mg/dL]	166 ± 32	169 ± 25	156 ± 19	170 ± 25	-13	<0.0001
Coefficient of Variation	37 ± 6%	36 ± 5%	34 ± 5%	36 ± 5%	-3%	<0.0001

1379 Overall, the studies using the AP algorithm originally developed at the University of Virginia, have

1380 logged >65,000 days of use to date, in 31 clinical trials enrolling over 600 children and adults with

1381 type 1 diabetes at 15 clinical centers in the U.S. and Europe (Table 1). Control IQ is the third

1382 commercial-grade generation of this algorithm, which will be used in this study.

1383 **15.3 Outcome Measures**

1384 **15.3.1 Primary Efficacy Endpoint**

To demonstrate the efficacy of Empagliflozin as adjuvant therapy added to a closed loop artificial pancreas system (AP-EMPA) in patients with T1DM. The primary efficacy outcome variable will be time in range (70-180 mg/dl). Secondary efficacy outcomes will be: time below 70 mg/dl, time above 180 mg/dl, time between 70-140 mg/dl 5 hours postprandial, glucose variability indices (HBGI, LBGI, ADRR). The corresponding variables obtained from the NO-AP-EMPA arm will be the comparator.

1391 **15.3.2 Secondary Outcome**

- 1392 To evaluate the safety of Empagliflozin as adjuvant therapy added to a closed loop artificial
- 1393 pancreas system (AP-EMPA) in subjects with T1DM by monitoring:
- 1394 Episodes of diabetic ketoacidosis (DKA)
- 1395 Episodes of severe hypoglycemia (glucose <50 mg/dl)
- 1396 Genital infections (balanitis, urethritis, vulvar infections, Fournier's gangrene)
- 1397 Urinary tract infections
- 1398 Other AE CGM based LBGI & HBGI
- 1399 Furthermore, we will compute
- 1400 Total amount of insulin used
- 1401 Number of hyperglycemic episodes as defined by contiguous CGM above 300mg/dL

1402 **15.4 Safety Analyses**

1403 All randomized participants will be included in these analyses and the circumstances of all 1404 reportable cases of the following will be summarized and tabulated by treatment group:

- 1405 Severe hypoglycemia
- 1406 Diabetic ketoacidosis
- 1407 Other serious adverse events and serious adverse device events
- 1408 Unanticipated adverse device effects

1409 **15.5 Baseline Descriptive Statistics**

- 1410 Baseline demographic and clinical characteristics of the cohort of all randomized participants will
- 1411 be summarized in a table using summary statistics appropriate to the distribution of each
- 1412 variable. Descriptive statistics will be displayed overall and by treatment group.
- 1413 Will include:
- 1414 Age
- 1415 HbA1c
- 1416 Gender
- 1417 Race/ethnicity
- 1418 CGM use before enrollment
- 1419 Diabetes duration
- 1420 BMI

1421 **15.6 Device Issues**

- 1422 The following tabulations and analyses will be performed by treatment group to assess device
- 1423 issues:
- 1424 Device malfunctions requiring study team contact and other reported device issues
- 1425 Sensor performance metrics (difference, absolute relative difference, and International
- 1426 Organization for Standardization criteria) if applicable, by sensor version.
- 1427 % time CGM data available overall and by month
- 1428 The following tabulations will be performed for the Experimental arm only:
- 1429 Performance metrics, describing the CLC system and its components like:
- a. % time CGM data were available to the CLC system overall and by month
- b. % time in different operational modes per week overall and by month
- 1432 c. Rate of different failure events and alarms per 48 hours recorded by the CLC
 1433 system overall and by month

Rationale for sample size determination: Use of Empagliflozin could potentially 'double the
effect' of Basal-IQ and Control IQ during the day by lowering postprandial glucose concentrations
based on the following rationale.

- 1437 a. Studies have demonstrated reduced hepatic glycogen synthesis resulting in 1438 reduced net hepatic glycogen content in poorly controlled T1D compared to 1439 nondiabetic controls [16]. In contrast, in well controlled T1DM subjects, initial 1440 splanchnic glucose uptake was not reduced when compared to matched 1441 nondiabetic controls [17]. Taken together, assuming usual daily carbohydrate intake of ~ 180 grams (i.e., 60 grams per main meal) in an adult with T1DM, and a 1442 net splanchnic extraction of ingested carbohydrates of ~ 25% [17], ~ 75% of 1443 1444 ingested carbohydrates (~ 135 grams) would appear daily into the circulation. 1445 Given a relatively conservative estimate that ~ half the ingested carbohydrates are taken up by the peripheral tissues, that leaves ~ 70 grams of ingested 1446 carbohydrates/day to contribute to postprandial glucose excursions. 1447
- 1448b. Based on data obtained from the prescribing information of Empagliflozin that 101449mg of Empagliflozin results in net urinary loss of 64 grams of glucose per day [18],1450it is reasonable to assume that adjuvant use of this medication with Control-IQ or1451Basal-IQ would at least "double the effects" of lowering postprandial glucose1452concentrations in this clinical trial.

1453 Chapter 16 Data Collection and Monitoring

1454 **16.1 Case Report Forms and Device Data**

The study data are collected through a combination of case report forms (electronic and paper) and electronic device data files obtained from the software and individual hardware components. These electronic device files and electronic CRFs are considered the primary source documentation.

1459 When data are directly collected in electronic case report forms, this will be considered the 1460 source data. Records will be maintained in accordance with ICH E6 and institutional regulatory 1461 requirements for the protection of confidentiality of participants.

1462 **16.2 Study Records Retention**

Study documents should be retained for a minimum of 2 years after the last approval of a marketing application in an ICH region and until there are no pending or contemplated marketing applications in an ICH region or until at least 2 years have elapsed since the formal discontinuation of clinical development of the investigational product. These documents should be retained for a longer period, however, if required by local regulations. No records will be destroyed without the written consent of the sponsor, if applicable. It is the responsibility of the sponsor to inform the investigator when these documents no longer need to be retained.

1470 **16.3 Protocol Deviations**

A protocol deviation is any noncompliance with the clinical trial protocol, Good Clinical Practices (GCP), or procedure requirements. The noncompliance may be either on the part of the participant, the investigator, or the study site staff. As a result of deviations, corrective actions may be developed by the site and implemented as appropriate. Major deviations will be reported

1475 to the IRB-HSR within 7 calendar days of when the study team becomes aware of the event.

1476 **Chapter 17 Ethics/Protection of Human Participants**

1477 **17.1 Ethics Standard**

The investigator will ensure that this study is conducted in full conformity with Regulations for
the Protection of Human Participants of Research codified in 45 CFR Part 46, 21 CFR Part 50, 21
CFR Part 56, and/or the ICH E6.

1481 **17.2 Institutional Review Boards**

The protocol, informed consent form(s), recruitment materials, and all participant materials will be submitted to the IRB for review and approval. Approval of both the protocol and the consent form must be obtained before any participant is enrolled. Any amendment to the protocol will require review and approval by the IRB before the changes are implemented to the study. All changes to the consent form will be IRB approved; a determination will be made regarding whether previously consented participants need to be re-consented.

1488 **17.3 Informed Consent Process**

1489 **17.3.1 Consent Procedures and Documentation**

1490 Informed consent is a process that is initiated prior to an individual's agreement to participate in 1491 the study and continues throughout the individual's study participation. Extensive discussion of 1492 risks and possible benefits of participation will be provided. Consent forms will be IRB approved 1493 and the participant will be asked to read and review the document. The investigator or their 1494 delegate will explain the research study to the participant and answer any questions that may 1495 arise. All participants will receive a verbal explanation in terms suited to their comprehension of 1496 the purposes, procedures, and potential risks of the study and of their rights as research 1497 participants. Participant will have the opportunity to carefully review the written consent form 1498 and ask questions prior to signing.

1499 The participant will sign the informed consent document prior to any procedures being done 1500 specifically for the study. A copy of the informed consent document will be given to the 1501 participant for their records. The rights and welfare of the participants will be protected by 1502 emphasizing to them that the quality of their medical care will not be adversely affected if they 1503 decline to participate in this study.

1504 **17.3.2 Participant and Data Confidentiality**

1505 The study monitor, representatives of the IRB or device company supplying study product may 1506 inspect all documents and records required to be maintained by the investigator, including but 1507 not limited to, medical records (office, clinic, or hospital) for the participants in this study.

1508 The study participant's contact information will be securely stored at the clinical site for internal 1509 use during the study. At the end of the study, all records will continue to be kept in a secure 1510 location for as long a period as dictated by local IRB and Institutional regulations.

1511 Study participant research data, which is for purposes of statistical analysis and scientific

1512 reporting, will be transmitted to and stored at the University of Virginia Center for Diabetes

1513 Technology. The study data entry and study management systems used by research staff will be

1514 secured and password protected. At the end of the study, all study databases may be de-

1515 identified and archived at the University of Virginia Center for Diabetes Technology.

1516 Chapter 18 References

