155 However, adverse effects pertaining to genital infections, diabetic ketoacidosis, and ketosis 156 without acidosis were between 2-3 fold higher with Empagliflozin than placebo. Due to the 157 glycosuric effects of this class of drugs, it is noteworthy that the characteristic hyperglycemic milieu often seen during classical episodes of diabetic keto-acidosis are not observed in 158 ketoacidosis related to SGLT2 drug use where the ambient glucose concentrations are frequently 159 < 250 mg/dl. This observation has prompted the creation of the condition of "euglycemic diabetic 160 keto-acidosis" associated with SGLT2 drug use. Risks for development of ketosis were deemed to 161 be due to concomitant illnesses (viral infections, gastro-enteritis), insulin pump failure, alcohol 162 excess, extreme/endurance sports and low carbohydrate diet (< 100 grams/day). Suggestions for 163 164 prevention of ketosis in patients on SGLT2 inhibitor therapy are to avoid use of this class of drugs 165 in those with HbA1c > 9%, temporary drug discontinuation for 24-48 prior to planned surgery, fasting, intercurrent illnesses or prolonged physical activity, early recognition of symptoms of 166 167 ketosis (malaise, nausea, vomiting, abdominal pain, excess thirst), regular point of care ketone 168 monitoring (6-12 hourly) especially if glucose > 9mmol. The putative STICH protocol has recently 169 been recommended for management of diabetic ketoacidosis associated with use of SGLT2 170 inhibitor therapy [9]. This includes **ST**op drug, Inject bolus insulin (1.5 times the usual correction 171 bolus), **C**onsume 30-60 grams of carbohydrate and **H**ydrate with 200-500 ml of fluids. The above 172 sequence needs to be repeated every 1-2 hours with recheck of ketones in 2-4 hours. Medical 173 attention should be sought if any of the steps cannot be followed, particularly if fluids cannot be 174 maintained or if ketonemia does not resolve within 4-6 hours.

The increased risk of ketosis and DKA in SGLT2 users with T1DM may not preclude use of this class of drugs for the management of T1DM given their clinical benefits in RCTs in T1DM patients (described above) and the cardiovascular benefits in T2DM patients. As always, careful patient selection, patient education and monitoring strategies need to be developed and tested to ensure patient safety.

180 **1.3 Artificial Pancreas with Empagliflozin (SGLT2-i) use in T1D**

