Adjuvant use of antidiabetic medications in combination with automated insulin delivery systems
 have been tested in short term clinical trials in T1DM. The drugs tested include pramlintide and
 GLP-1 receptor agonists [6]. To the best of our knowledge, there are no published clinical trials
 on the safety and efficacy of combining SGLT2 inhibitors with closed loop control. In contrast to

185 the above trials, where both pramlintide and GLP-1 agonists need to be infused or injected, 186 Empagliflozin, an SGLT2 inhibitor, is taken as a once daily oral tablet making it simple, practical 187 and not burdensome for patient adherence. Additionally, given its proven benefits on glucose 188 control in several large RCTs involving >1700 patients with T1DM, it is necessary to test its efficacy 189 and safety, in combination with automated insulin delivery systems, in T1DM subjects as part of 190 a clinical trial that we propose. Additionally, albeit the increased prevalence of ketosis with 191 empagliflozin use in the published trials, given the accumulated clinical information and 192 experience, we will ensure that appropriate precautions including judicious selection of research 193 participants (HbA1c of 9% as cutoff for enrollment), educating subjects on avoiding 194 circumstances that could predispose to ketosis (intercurrent illnesses, alcohol excess, low carb diet etc) and careful monitoring, will prevent and further lower the risks of ketosis during the 195 196 proposed, short term clinical trial.

197 **1.4 Basal-IQ with Empagliflozin use in T1D**

The Basal-IQ feature in the t:slim insulin pump reduce the frequency and duration of low-glucose events by predicting glucose levels 30 minutes ahead and suspending insulin if they are expected to drop below 80 mg/dL. Use of Empagliflozin during Basal-IQ phase is to explore its safety and feasibility as an adjunctive agent, compare its use vs Control-IQ phase and to gather data on its effect on postprandial glucose excursions.

203 **1.5 Study Objective**

[figure not shown]
The purpose of this study is to demonstrate the safety and efficacy of the use of Empagliflozin as
an adjunctive therapy with the Tandem t:slim X2 insulin pump with Control IQ Technology vs.
the Tandem t:slim X2 insulin pump with Basal-IQ Technology in T1D participants.

207 **1.6 Study Design**

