- 347 10. Willingness to switch to lispro (Humalog) or aspart (Novolog) if not using already, and to use
 348 no other insulin besides lispro (Humalog) or aspart (Novolog) during the study
- 349 11. Total daily insulin dose (TDD) at least 10 U/day
- Willingness not to start any new non-insulin glucose-lowering agent during the course of the
 trial (including metformin, GLP-1 agonists, pramlintide, DPP-4 inhibitors, biguanides,
 sulfonylureas and naturaceuticals)
- 13. Willingness to eat at least 100 grams of carbohydrates per day
- 14. An understanding and willingness to follow the protocol and signed informed consent
- 355 15. *Pilot Participants:* Agree to hotel/research house admission with other Pilot participants on
 a date selected by the study team.

357 **4.5 Participant Exclusion Criteria**

- The participant must not have any exclusion criteria in order to be eligible to participate in the study.
- 360 1. Hemoglobin A1c >9%

- 361 2. History of diabetic ketoacidosis (DKA) in the 12 months prior to enrollment
- 362 3. Severe hypoglycemia resulting in seizure or loss of consciousness in the 12 months prior to363 enrollment
- 364 4. Pregnancy or intent to become pregnant during the trial
- 365 5. Currently breastfeeding or planning to breastfeed
- 366 6. Currently being treated for a seizure disorder
- 367 7. Planned surgery during study duration
- 368 8. History of cardiac arrhythmia (except for benign premature atrial contractions and benign369 premature ventricular contractions which are permitted)
- 370 9. Clinically significant electrocardiogram (ECG) abnormality at time of Screening, as interpreted371 by the study medical physician
- 372 10. Use of diuretics (e.g. Lasix, Thiazides)
- 373 11. History of chronic or recurrent genital infections
- 12. eGFR lab value below 60 mL/min/1.73 m2
- 13. Treatment with any non-insulin glucose-lowering agent (including metformin, GLP-1 agonists,
 pramlintide, DPP-4 inhibitors, SGLT-2 inhibitors, biguanides, sulfonylureas and
 naturaceuticals)
- 378 14. A known medical condition that in the judgment of the investigator might interfere with the379 completion of the protocol such as the following examples:
- 380 a. Severe renal impairment, end-stage renal disease, or dialysis
- b. Inpatient psychiatric treatment in the past six months
- 382 c. Presence of a known adrenal disorder

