- 383 d. Abnormal liver function test results (Transaminase>2 times the upper limit of 384 normal); testing required for subjects taking medications known to affect liver 385 function or with diseases known to affect liver function
- e. Uncontrolled thyroid disease
- 387 15. Severe renal impairment, end-stage renal disease, or dialysis
- 16. Use of an automated insulin delivery mechanism that is not downloadable by the subject orstudy team
- 390 17. Current enrollment in another clinical trial, unless approved by the investigator of both391 studies or if clinical trial is a non-interventional registry trial
- 392 18. Alcohol restricted to no more than 2 drinks per night in men and no more than 1 drink per393 night in women
- 19. Low carb diet (less than 100g per day)

395 **4.6 Eligibility Screening Procedures**

- The participant will be evaluated for study inclusion and exclusion eligibility after the informed consent form has been signed by the participant and the study team.
- Individuals who do not initially meet study eligibility requirements may be rescreened at a laterdate per investigator discretion.

400 1. Demographics

401 a. Date of birth 402 b. Gender 403 c. Race 404 d. Ethnicity 405 2. Medical History 406 a. Duration of disease (number of years) 407 b. Current insulin pump model 408 c. History of CGM use 409 d. Current treatment 410 i. **Basal rates** 411 ii. Carbohydrate ratios 412 iii. Insulin sensitivity factors 413 iv. Target glucose Average daily insulin 414 v. 415 e. History of diabetic ketoacidosis 416 f. History of severe hypoglycemia 417 g. History of seizures h. Loss of consciousness 418 419 3. Surgical history 4. Allergies 420 421 5. Concomitant medications 422 6. Physical Examination – A historical history and physical report within 52 weeks of the 423 screening appointment may be used 424 a. Weight 425 b. Height 426 c. Blood pressure d. Pulse 427 428 e. Temperature

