1026 Based on the facts that (1) adults and adolescents with diabetes experience mild hypoglycemia 1027 and hyperglycemia frequently as a consequence of the disease and its management, (2) the study 1028 intervention involves periodic automated insulin dosing that may increase the likelihood of 1029 hypoglycemia, and periodic automated attenuation of insulin delivery that may increase the 1030 likelihood of hyperglycemia, (3) mitigations are in place, and have been tested in prior studies 1031 using the investigational device system in the home setting, that limit the likelihood of excessive 1032 insulin dosing or prolonged withdrawal of insulin, and (4) rapid reversal of hypoglycemia and 1033 hyperglycemia can be achieved, it is the assessment of the investigators that this protocol falls 1034 under DHHS 46.405 which is a minor increase over minimal risk. In addition, it is the belief of the 1035 investigators that this study also presents prospect of direct benefit to the participants and general benefit to others with diabetes. 1036

1037 12.2 Potential Risks and Benefits of the Medication

1038 **12.2.1 Empagliflozin Adverse Reactions**

1039 The most recognized adverse reactions associated with the use of Empagliflozin are urinary tract 1040 infections and mycotic genital infections occurring in both men and women.

1041 Nausea, vomiting, abdominal pain, generalized malaise, acute febrile illness, reduced caloric 1042 intake due to illness or surgery, alcohol abuse, and shortness of breath may result in adverse 1043 reactions. The study physician may consider temporarily discontinuing Empagliflozin in any 1044 setting of reduced oral intake (such as acute illness or fasting) or fluid losses (such as 1045 gastrointestinal illness or excessive heat exposure).

After initiating therapy, participants will be monitored for increased urination and dehydration.
Participants will be informed that dehydration may increase the risk of hypotension and,
therefore, will be encouraged to increase their fluid intake while taking the medication.
Participates will also be advised that a majority of infections can be prevented by maintaining
attention to basic hygiene include regular washing after urination.

1051 Ketoacidosis is a common adverse reaction with the use of Empagliflozin. Ketone measurement1052 instructions are detailed in section 10.5.

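### Exclusion 18 is worded in reverse: read literally, it bars people within the alcohol limit and does not exclude those above it

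*Combined protocol and SAP*

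**What the plan says.** Section 4.5 sets the rule for its whole list: "The participant must not have any exclusion criteria in order to be eligible". Item 18 of that list is "Alcohol restricted to no more than 2 drinks per night in men and no more than 1 drink" per night in women. It does not say whether this describes usual intake at screening or a restriction to be kept during the study.

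The protocol mentions alcohol as a hazard in three other places:

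- Section 1.2 names alcohol excess among the causes of ketosis with this drug class.
- Section 1.3 says participants will be educated to avoid "circumstances that could predispose to ketosis (intercurrent illnesses, alcohol excess, low carb diet etc".
- Section 12.2.1 lists alcohol abuse among the conditions that may lead to adverse reactions: "intake due to illness or surgery, alcohol abuse, and shortness of breath may result in adverse" reactions.

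The neighbouring carbohydrate rule is a useful comparison. Exclusion 19 is "Low carb diet (less than 100g per day", and inclusion 13 is "Willingness to eat at least 100 grams of carbohydrates per day".

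**The concern.** An exclusion item should describe the state that makes a person ineligible. Item 18 describes permitted behaviour. It reads like a conduct restriction that has been placed in the exclusion list.

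Two things are at stake. If the text is followed literally, screening works against a risk that the protocol itself identifies. If staff follow the presumed intent, they depart from the written criterion, and eligibility can no longer be audited against it. Section 16.3 counts any noncompliance with the protocol as a deviation, so enrolling a person within the limit would be a deviation as the text stands.

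**Working it through.** No calculation applies, and the plan gives no figure to reproduce. The check is one of logical direction, followed by a search for anything that corrects it.

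**Step 1: apply the lead-in of 4.5 to item 18.** The limits are those in the item, and the intakes follow from them.

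| Usual drinks per night | Meets item 18 as worded? | Result under the 4.5 lead-in |
|---|---|---|
| Man, 0 to 2 | Yes | Ineligible |
| Man, 3 or more | No | Not excluded by this item |
| Woman, 0 to 1 | Yes | Ineligible |
| Woman, 2 or more | No | Not excluded by this item |

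**Step 2: compare with the stated risk.** Sections 1.2, 1.3 and 12.2.1 attach the hazard to excess or abuse. The literal result in step 1 therefore points the opposite way.

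**Step 3: compare with exclusion 19.** Sections 1.2 and 1.3 name low carbohydrate intake alongside alcohol excess as a ketosis risk. Exclusion 19 names the risk state itself, so meeting it correctly makes a person ineligible, and inclusion 13 adds the matching commitment. Item 18 names the safe state and has no matching commitment. The same page thus shows how such a rule is meant to be built.

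**Step 4: look for a correction elsewhere.** None of the 15 inclusion items and none of the other 18 exclusion items mentions alcohol. Three general provisions remain:

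- Section 4.2 has the inclusion and exclusion questions asked at prescreening. A question taken from item 18 as worded carries the same reversal.
- Inclusion 14 asks for willingness to follow the protocol. It does not name alcohol, and it does not change the effect of an item in the exclusion list.
- Section 4.6 lets the study physician exclude someone on safety grounds. This is optional and has no alcohol criterion.

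All three are partial backstops, and none restores the direction of the rule.

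**Step 5: look for an effect on the analysis.** Eligibility is settled before randomization (Chapter 5) and item 18 applies to all four groups alike. The wording therefore does not bias the comparison of Empagliflozin with no Empagliflozin. It also does not enter the sample size, power or type 1 error in Chapter 15. What it affects is who may enter.

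**The case against.** The strongest reply is that nobody would apply the item literally. Barring moderate drinkers while accepting heavy ones is absurd, the trial has a single site (section 1.7.2), and its staff would notice at once. That largely stands, and it limits the practical risk. It does not make the written criterion correct.

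The reply is also right against several stronger readings that a reader might draw:

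- *That the safety argument in 1.3 depends on selecting by alcohol intake.* It does not. Section 1.3 ties selection to the HbA1c cutoff and deals with alcohol through education.
- *That alcohol intake is never asked about.* The medical history list in 4.6 has no alcohol item, but 4.2 provides for criteria questions at prescreening. The 4.6 list does not itemise carbohydrate intake either, so its silence is not specific to alcohol.
- *That the error threatens the stopping limits in 8.3.* One event among 20 drug-arm participants is 1/20 = 5%, which invites comparison with the DKA limit. But that limit is more than 5%, so exactly 5% does not cross it. Milder ketosis has its own limits of 40% and 20%. The reviews in 8.3 come after 10 participants, not after 20 on the drug. Nothing in the documents links a number of events to item 18.

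**Conclusion.** Item 18 is wrong as written. It is an operative eligibility rule that gives the reverse of the result implied by sections 1.2, 1.3 and 12.2.1, and no other criterion repairs it. The safety bearing is modest, and its size cannot be put into numbers: the documents give no distribution of alcohol intake among applicants and no ketosis rate by intake.

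The conclusion rests on reading the 4.5 lead-in as applying to every item in its list, which is what it says. It does not assume that staff would follow the literal text. A reader might infer that heavy drinkers will in fact be enrolled and light drinkers turned away. The documents do not support that, because actual misclassification depends on how staff read the item and they would probably infer the intent.

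**What to change.** Reconcile item 18 with sections 1.2 and 1.3:

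- If it is an entry criterion, reword it as the excluded state, that is, usual intake exceeding the limit already stated in the item, and say that it is judged at screening.
- If it is a rule for conduct during the study, move it to 4.4 as a willingness item parallel to no. 13.
- If both are meant, state both, as is done for carbohydrate.

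The numeric limit remains the sponsor's, and this point takes no view on it. An alcohol line in the 4.6 history list would be convenient but is a matter of preference.

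The cost is one or two lines of protocol text and the IRB review that section 17.2 requires for any amendment. Sample size, error rates and analyses are unchanged.
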